To support regulatory filings, interim analyses may be conducted based on efficacy, safety, PK, PD, and immunogenicity data collected through the end of the 26-week Primary Evaluation Period (Day 183) after 12 patients are enrolled, and after enrollment is completed.

After completion of all pre-dose assessments on Day 183, all patients will enter an Extension Period and continue to receive ALXN1210 according to the appropriate weight-based regimen. The Extension Period will continue until the product is registered or approved (in accordance with country-specific regulations) or for up to 4 years, whichever occurs first, except in Norway where the Extension Period will be 4 years. The end of study is defined as the last patient's last visit or follow-up (whether on site or via phone call) in the Extension Period

Number of Patients (planned): Approximately 13 patients, from birth to < 18 years, will be enrolled to ensure at least 10 evaluable patients complete the 26-week period.

Diagnosis and Main Criteria for Inclusion and Exclusion:

Patients must meet all inclusion and no exclusion criteria. Patients who fail any of the eligibility criteria may be rescreened once for participation.

Inclusion Criteria:

- 1. Male and female patients < 18 years of age and weighing ≥ 5 kg at the time of consent.
- 2. Documented diagnosis of PNH, confirmed by high-sensitivity flow cytometry evaluation of red blood cells (RBCs) and white blood cells (WBCs), with granulocyte or monocyte clone size of \geq 5%.
- 3. For patients not currently treated with complement inhibitor, presence of 1 or more of the following PNH-related signs or symptoms within 3 months of Screening: fatigue, hemoglobinuria, abdominal pain, shortness of breath (dyspnea), anemia, history of a major adverse vascular event (including thrombosis), dysphagia, or erectile dysfunction; or history of packed RBC transfusion due to PNH.

- 4. Lactate dehydrogenase (LDH) values at Screening as follows:
 - a. For patients not currently treated with eculizumab, LDH level $\geq 1.5 \times \text{upper limit of normal}$ (ULN).
 - b. For patients who are currently taking eculizumab, LDH ≤ 1.5× ULN (sample must be obtained on a scheduled eculizumab-dosing day prior to dose administration [ie, at trough eculizumab level] and analyzed by the central laboratory).

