8.1. Inclusion Criteria

Patients are eligible for enrollment in the study only if they meet all of the following criteria and none of the exclusion criteria:

- 1. Male and female patients < 18 years of age and weighing ≥ 5 kg at the time of consent.
- 2. Documented diagnosis of PNH, confirmed by high-sensitivity flow cytometry evaluation (Borowitz, 2010) of red blood cells (RBCs) and white blood cells (WBCs), with granulocyte or monocyte clone size of \geq 5%.
- 3. For patients not currently treated with eculizumab, presence of 1 or more of the following PNH-related signs or symptoms within 3 months of Screening: fatigue, hemoglobinuria, abdominal pain, shortness of breath (dyspnea), anemia, history of a major adverse vascular event (including thrombosis), dysphagia, or erectile dysfunction; or history of packed red blood cell (pRBC) transfusion due to PNH.
- 4. Lactate dehydrogenase (LDH) values at Screening as follows:
 - a. For patients not currently treated with eculizumab, LDH level $\geq 1.5 \times \text{ULN}$.
 - b. For patients who are currently taking eculizumab, LDH $\leq 1.5 \times$ ULN (sample must be obtained on a scheduled eculizumab-dosing day prior to dose administration [ie, at trough eculizumab level] and analyzed by the central laboratory).
- 5. To reduce the risk of meningococcal infection (*N meningitidis*), all patients must be vaccinated against meningococcal infections within 3 years prior to, or at the time of, initiating study drug. Patients who initiate study drug treatment less than 2 weeks after receiving a meningococcal vaccine must receive treatment with appropriate prophylactic antibiotics until 2 weeks after vaccination. Patients who cannot be vaccinated must receive antibiotic prophylaxis for the entire treatment period and for 8 months following last dose.
- 6. Patients must have been vaccinated against *Haemophilus influenzae* type b (Hib) and *Streptococcus pneumoniae* according to national and local vaccination schedule guidelines, as appropriate.
- 7. Female patients of childbearing potential (ie, have achieved menarche) and male patients with female partners of childbearing potential must follow protocol-specified guidance for avoiding pregnancy while on treatment and for 8 months after last dose of study drug.

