9.1.4. Study Drug Preparation and Infusion

ALXN1210 must NOT be administered as an IV push or bolus injection. Infusions of study drug must be prepared using aseptic technique. The patient's required dose of ALXN1210 will be further diluted into commercially available saline (0.9% sodium chloride; country-specific pharmacopeia) at the volume specified in Table 5. ALXN1210 admixture will be administered to the patient using an IV tubing administration set via an infusion pump. Use of a 0.2 micron filter is required during infusion of ALXN1210.

Table 5:	Dosing Reference Chart for ALXN1210 Dose Preparation
----------	---

Dose Type	Body Weight (kg) ^a	Dose (mg)	ALXN1210 Volume (mL)	Saline Volume (mL)	Total Volume (mL)	Minimum Infusion Duration minutes (hours)	Maximum Infusion Rate (mL/hour)
Loading	\geq 5 to < 10	600	60	60	120	228 (3.8)	31.5
	$\geq 10 \text{ to} < 20$	600	60	60	120	113 (1.9)	63.1
	\geq 20 to < 30	900	90	90	180	86 (1.5)	120.0
	\geq 30 to < 40	1200	120	120	240	77 (1.3)	184.6
	\geq 40 to < 60	2400	240	240	480	114 (1.9)	253
	\geq 60 to < 100	2700	270	270	540	102 (1.7)	318
	≥ 100	3000	300	300	600	108 (1.8)	333
Maintenance	\geq 5 to < 10	300	30	30	60	113 (1.9)	31.5
	$\geq 10 \text{ to} < 20$	600	60	60	120	113 (1.9)	63.1
	\geq 20 to < 30	2100	210	210	420	194 (3.3)	127.2
	\geq 30 to < 40	2700	270	270	540	167 (2.8)	192.8
	\geq 40 to < 60	3000	300	300	600	140 (2.4)	250
	\geq 60 to < 100	3300	330	330	660	120 (2.0)	330
	≥ 100	3600	360	360	720	132 (2.2)	328

Note: Please refer to the Pharmacy Manual for additional dose preparation instructions.

Doses of study drug must only be prepared and dispensed by qualified study personnel. Study drug is to be dispensed only to enrolled patients who are confirmed eligible for participation in this study. Once study drug is prepared for a patient, it can only be administered to that patient. Vials of study drug are for one-time use only and any drug product remaining in the vial should not be used for another patient. Any drug remaining in the infusion tubing or infusion bag should not be used for another patient.

Further details on preparation and dose administration of study drug, as well as disposal of study drug, can be found in the Pharmacy Manual.

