9.2. Treatments Administered

Patients will receive a loading dose of ALXN1210 on Day 1, followed by maintenance dosing of ALXN1210 on Day 15 and q8w thereafter for patients weighing \geq 20 kg, or q4w for patients weighing \leq 20 kg, as shown in Table 6. With the agreement of the Alexion Medical Monitor, the 600 mg loading dose may be given to patients weighing \geq 5 to \leq 10 kg as 2 separate infusions administered no more than 24 hours apart. Dosages are based on the patient's body weight recorded on the day of dosing or the most recently recorded weight. For patients entering the study on eculizumab therapy, Day 1 of study treatment will occur 2 weeks from the patient's last dose of eculizumab.

Table 6:	Loading and Maintenance Treatment Regimen	IS

Body Weight Range (kg) ^a	Loading Dose (mg)	Maintenance Doses (mg)	Maintenance Dosing Frequency
\geq 5 to < 10	600 ^b	300	q4w
$\geq 10 \text{ to} < 20$	600	600	q4w
\geq 20 to < 30	900	2100	q8w
\geq 30 to < 40	1200	2700	q8w
\geq 40 to < 60	2400	3000	q8w
\geq 60 to < 100	2700	3300	q8w
≥ 100	3000	3600	q8w

Abbreviations: q4w = once every 4 weeks; q8w = once every 8 weeks

With the agreement of the Alexion Medical Monitor, administration of a supplemental dose of ALXN1210 is permitted.

After the Primary Evaluation Period, all patients will roll over into an Extension Period and continue their weight-based maintenance dose of ALXN1210 on Day 183 and q8w thereafter for patients weighing ≥ 20 kg, or q4w for patients weighing ≤ 20 kg, until the product is registered or approved (in accordance with country specific regulation) or for up to 4 years, whichever occurs first, except in Norway where the Extension Period will be 4 years.

The actual time of all dose administrations, including any supplemental dose or dose administered as 2 separate infusions as noted above, will be recorded on the patient's eCRF.

^a Dose regimen will be based on body weight obtained at the study visit. If the study drug needs to be prepared the night prior to the visit, the weight from the previous visit may be used.

b With the agreement of the Alexion Medical Monitor, the 600 mg loading may be given to patients weighing ≥ 5 to < 10 kg as 2 separate infusions administered no more than 24 hours apart.

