APPENDIX B. MANAGEMENT OF POTENTIAL DRUG INFUSION REACTIONS

Infusion of other monoclonal antibodies has been associated with infusion reactions, with onset typically during or shortly after completion of the infusion. For this reason, patients will be carefully observed during each infusion.

Patients who develop AEs of rash, hives, itching, or dysphagia of mild to moderate intensity during their infusion of ALXN1210 may continue to receive the infusion if deemed to be medically appropriate by the Investigator. Medical intervention may include, but is not limited to, slowing of the infusion rate (with or without treatment) or interrupting or stopping the infusion.

Any acute reaction should be treated according to standard medical practice depending upon clinical signs and symptoms. If a patient requires medical intervention, the patient should remain at the investigational site until his or her condition stabilizes. The AE and any associated concomitant medications must be captured on the patient's source document and electronic case report form (eCRF).

Some patients treated with IV infusions of monoclonal antibodies have experienced concurrent reactions with signs or symptoms that can be classified as acute allergic reactions/hypersensitivity reactions or cytokine release syndrome. Signs and symptoms include headache, fever, facial flushing, pruritus, myalgia, nausea, chest tightness, dyspnea, vomiting, erythema, abdominal discomfort, diaphoresis, shivers, hypertension, lightheadedness, hypotension, palpitations, and somnolence. Anaphylaxis might occur at any time during an infusion; therefore, patients will be monitored closely during the infusion. In addition, the re-administration of some monoclonal antibodies has been associated with serum sickness-like reactions manifesting 1 to 14 days after drug administration. All AEs that may indicate an infusion-related response will be graded according to the CTCAE v4.03 or higher.

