Before any infusion is started, the treating physician and other appropriate personnel must make certain that medication (ie, adrenaline, inhaled beta agonists, antihistamines, corticosteroids) and other equipment to treat anaphylaxis are readily available. The infusion must be stopped immediately if Grade ≥ 2 allergic/hypersensitivity reactions (including drug fever) or Grade ≥ 3 cytokine release syndrome/acute infusion reaction occurs. The Sponsor must be notified within 24 hours of any infusion reaction requiring interruption or discontinuation of study drug.

Patients who experience a reaction during the administration of study drug should be treated according to institutional guidelines. For a Grade 1 or Grade 2 infusion reaction, the infusion should be temporarily stopped and treatment with an antihistamine (eg, diphenhydramine 25 to 50 mg orally or equivalent) and acetaminophen (650 mg orally or equivalent) may be considered. If the patient's signs and symptoms have resolved (with or without administration of the above medication), the infusion may be restarted. However, the patients should be infused at a slower rate and be monitored closely for any signs and symptoms of infusion reactions during the remainder of the infusion. Patients experiencing an infusion reaction should be observed in the clinic until resolution of the reaction, or until the Investigator determines the patient is no longer at risk. Patients who experience a severe reaction during administration of study drug resulting in discontinuation of study drug should undergo all scheduled safety, PK, and PD evaluations required by the protocol.

If anaphylaxis occurs according to the criteria listed below, then administration of subcutaneous epinephrine (1/1000, 0.3 mL to 0.5 mL, or equivalent) should be considered. In the case of bronchospasm, treatment with an inhaled beta agonist also should be considered. Patients administered an antihistamine for the treatment or prevention of an infusion reaction should be given appropriate warnings about drowsiness and impairment of driving ability before being discharged from the center.

Clinical Criteria for Diagnosing Anaphylaxis:

Anaphylaxis is highly likely when any 1 of the following 3 criteria is fulfilled:

- Acute onset of an illness (minutes to several hours) with involvement of the skin, mucosal tissue, or both (eg, generalized hives, pruritus or flushing, swollen lips-tongue-uvula), and at least 1 of the following:

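### Appendix B prints amounts of three medicines for infusion reactions with no weight or age term, in a protocol that enrols from birth and from 5 kg

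*Protocol*

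**What the plan says.** Protocol Appendix B covers the management of infusion reactions. For a Grade 1 or Grade 2 reaction the infusion is paused, and treatment with an "antihistamine (eg, diphenhydramine 25 to 50 mg orally or equivalent) and acetaminophen (650 mg orally or equivalent) may be considered". For anaphylaxis, "administration of subcutaneous epinephrine (1/1000, 0.3 mL to 0.5 mL, or equivalent) should be considered".

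The appendix also defers to local practice. In general, "Any acute reaction should be treated according to standard medical practice depending upon clinical signs and symptoms". For reactions during administration, "Patients who experience a reaction during the administration of study drug should be treated according to institutional guidelines"; the antihistamine and acetaminophen amounts follow in the very next sentence.

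On population, the Synopsis states "Approximately 13 patients, from birth to < 18 years, will be enrolled", and Section 8.1 admits "Male and female patients < 18 years of age and weighing ≥ 5 kg at the time of consent". Section 9.2 sets the study-drug dose by "body weight recorded on the day of dosing or the most recently recorded weight", in seven weight bands. Section 9.1.4 (Table 5) sets the maximum infusion rate by the same bands, and Appendix A caps blood loss per kg.

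Section 9.10 names Appendix B, together with a home health care manual, as the source for managing reactions during home infusions.

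**The concern.** The protocol scales study drug, infusion rate and blood sampling to body weight, but the three reaction medicines are given as one amount or range for every patient. Used as written, the lightest child would receive the most per kg. This is safety text that may be consulted in an emergency.

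Appendix B does not say which prevails if a printed amount and an institutional guideline differ. If local guidelines are meant to govern, the amounts add nothing; if the amounts are meant to help, they are not fitted to the enrolled weight range. The appendix also asks staff to warn patients given an antihistamine about driving. That suggests, without proving it, that the text was not adapted for young children.

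The stake is patient safety only. No endpoint, analysis set or planned summary depends on these amounts.

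**Working it through.** The plan states no per-kg figure for these medicines, so there is none to reproduce. The check is a search for any adjusting text, followed by division.

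**Search.** No section of the protocol or SAP gives a per-kg amount, age band or pediatric maximum for diphenhydramine, acetaminophen or epinephrine.

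**Inputs**
- Appendix B: diphenhydramine 25 to 50 mg; acetaminophen 650 mg; epinephrine 1/1000, 0.3 to 0.5 mL. Reading 1/1000 as 1 mg/mL, this is 0.3 to 0.5 mg.
- Section 9.2, Table 6: lower edges of the seven weight bands, w = 5, 10, 20, 30, 40, 60 and 100 kg.

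**Formula.** Amount per kg = printed amount / w.

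| w (kg) | Acetaminophen, 650/w (mg/kg) | Diphenhydramine, 25/w to 50/w (mg/kg) | Epinephrine, 0.3/w to 0.5/w (mg/kg) |
|---|---|---|---|
| 5 | 130 | 5 to 10 | 0.06 to 0.10 |
| 10 | 65 | 2.5 to 5 | 0.03 to 0.05 |
| 20 | 32.5 | 1.25 to 2.5 | 0.015 to 0.025 |
| 30 | 21.7 | 0.83 to 1.67 | 0.010 to 0.017 |
| 40 | 16.3 | 0.63 to 1.25 | 0.0075 to 0.0125 |
| 60 | 10.8 | 0.42 to 0.83 | 0.005 to 0.008 |
| 100 | 6.5 | 0.25 to 0.5 | 0.003 to 0.005 |

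**Spread.** Because the amounts do not depend on weight, the per-kg ratio is the weight ratio: 100/5 = 20 at the extremes, and 60/20 = 3 without them.

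**Comparison with quantities the protocol does scale**
- Maximum loading infusion rate (Table 5): 120.0/20 = 6.0 and 318/60 = 5.3 mL/h/kg, a ratio of 1.13. At the extremes, 31.5/5 = 6.3 and 333/100 = 3.33 mL/h/kg, a ratio of 1.9.
- Loading dose (Table 6): 900/20 = 45 and 2700/60 = 45 mg/kg, a ratio of 1. At the extremes, 600/5 = 120 and 3000/100 = 30 mg/kg, a ratio of 4.
- Four-week blood-loss limit (Appendix A): 2.4 mL/kg at every weight, a ratio of 1.

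The protocol's own banded figures are thus not constant per kg, but their spread is well below that of the three medicines over the same weights.

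**The case against.** The strongest reply is that Appendix B is guidance and clinicians decide. Section 9.5 describes it as guidance. Section 9.7 leaves medication for an adverse event to the investigator's discretion, and Section 9.9 requires supervised administration. The amounts are only to be considered and allow an equivalent. Home infusions under Section 9.10 are confined to the COVID-19 period and to patients who tolerated earlier on-site infusions well. A qualified professional conducts remote visits, and the home manual may already give pediatric amounts. Rescue medication is clinical care, which a protocol need not dose as it doses study drug. The fold-differences are merely weight ratios, and whether a given mg/kg matters can be judged only from sources outside the documents.

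Much of this stands. No one is required to give these amounts, the ratios do not measure risk, and the contents of the home manual are unknown.

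It does not remove the point. None of these provisions supplies a weight or age term. Wording that a medicine may be considered governs whether to give it, not how much. Allowing an equivalent to a stated amount is most naturally read as permitting another product. The example marker stands before diphenhydramine only, not before acetaminophen or epinephrine. The deferral to local guidelines argues for deleting the amounts as much as for tolerating them.

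**Conclusion.** The concern holds. Three amounts are printed without a weight or age term in a protocol open to patients from birth and from 5 kg, and nothing in either document adjusts them. It is an internal inconsistency in safety wording, not an instruction to overdose, and it should be fixed at the next amendment.

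The per-kg figures are conditional on a clinician using an optional amount as printed, and the epinephrine figures also on reading 1/1000 as 1 mg/mL. The 5 and 100 kg values are the lowest permitted weight and the lower edge of the top band. The documents give no expected weight distribution for the approximately 13 patients, so the number of very light children is unknown. The 3-fold range from 20 to 60 kg does not rely on those extremes. No claim is made about toxicity or the likelihood of harm.

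**What to change.** In the next amendment, change the two sentences of Appendix B that carry the amounts, in one of two ways:

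1. Delete all three amounts and refer to institutional guidelines appropriate to the patient's age and weight.
2. Have the sponsor's medical staff restate all three by weight.

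No dose is proposed here; that is a medical decision. Either way, check that the home health care manual, which was not available, agrees with the revised appendix.

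The cost is the wording of two sentences and one consistency check. Visits, samples and analyses do not change.

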APPENDIX C. PEDIATRIC FACIT-FATIGUE

Pediatric (Paediatric) Functional Assessment of Chronic Illness Therapy – Fatigue

Header to be completed by study site					
	Study Number: ALXI	N1210-PNH-304	Subject ID:		
	Date Completed:		Time Completed:		
	Completed by: Patient	Caregiver (Initials):			

Below is a list of statements that other people with your illness have said are important. Please circle or mark one number per line to indicate your response as it applies to the past 7 days.

	1	None of the	A little bit of	Some of the	Most of the time	All of the
		time	the time	time		time
pF1	I feel tired	0	1	2	3	4
pF2	I have energy (or strength)	0	1	2	3	4
pF3	I could do my usual things at home	0	1	2	3	4
pF4	I had trouble starting things because I was too tired	0	1	2	3	4
pF5	I had trouble finishing things because I was too tired	0	1	2	3	4
pF6	I needed to sleep during the day	0	1	2	3	4
pF7	I got upset by being too tired to do things I wanted to do.	0	1	2	3	4
pF8	Being tired made it hard for me to play or go out with my friends as much as I'd like	0	1	2	3	4
pF9	I needed help doing my usual things at home	0	1	2	3	4
pF10	I feel weak	0	1	2	3	4
pF11	I was too tired to eat	0	1	2	3	4
pF12	Being tired made me sad	0	1	2	3	4
pF13	Being tired made me mad (angry)	0	1	2	3	4

Engisia (Universal)
22 June 2016
Copyright 1887, 1997, 2006
Page 1 of 1

APPENDIX D. PROTOCOL LABORATORY TESTS

Hematology

Free hemoglobin Haptoglobin Hematocrit Hemoglobin

Mean corpuscular hemoglobin

Platelet count RBC count

RBC distribution width

RBC mean corpuscular volume

Reticulocyte count WBC count WBC differential

Coagulation Panel

International normalized ratio Partial thromboplastin time

Prothrombin time

Urinalysis

Appearance
Bilirubin
Blood
Color
Glucose
Ketone
Nitrite
pH
Specific gravity

Urine Chemistry

Urobilinogen

Microalbumin

Clinical Chemistry

Alanine aminotransferase

Albumin

Alkaline phosphatase Aspartate aminotransferase

Bicarbonate

Blood urea nitrogen

Calcium Chloride Creatinine

Gamma-glutamyltransferase

Glucose

Lactate dehydrogenase

Magnesium Phosphorus Potassium Sodium

Total bilirubin (direct and indirect)

Total protein Uric acid

Other

Antidrug antibody

Beta human chorionic gonadotropin (females of

childbearing potential only)

Chicken RBC assay Free and total C5 Pharmacokinetic assay PNH clone size

Abbreviations: C5 = complement component 5; PNH = paroxysmal nocturnal hemoglobinuria; RBC = red blood cell; WBC = white blood cell

3. LIST OF ABBREVIATIONS AND DEFINITIONS OF TERMS

The following abbreviations and acronyms are used in this SAP.

Table 1: Abbreviations and acronyms

Abbreviation or acronym	Explanation
ADA	antidrug antibody
AE	adverse event
AESI	adverse event of special interest
ALT	alanine aminotransferase (SGPT)
ATC	Anatomical Therapeutic Chemical
AST	aspartate aminotransferase (SGOT)
AUC _t	area under the serum concentration-versus-time-curve from time 0 (dosing) to the last quantifiable concentration
AUC _{0-τ}	area under the concentration-versus-time-curve from time 0 (dosing) to the end of the dosing interval
BMI	body mass index
cm	centimeters
BNP	brain natriuretic peptide
BP	blood pressure
CAP	complement alternative pathway
CKD	chronic kidney disease
CI	confidence interval
CL	total clearance
C _{max}	maximum observed serum concentration
C _{min}	minimum observed serum concentration
cRBC	chicken red blood cell
CS	clinically significant
CSR	Clinical Study Report
CTCAE	Common Terminology Criteria for Adverse Events
CV	coefficient of variance
DMC	Data Monitoring Committee
ECG	electrocardiogram
eCRF	electronic case report form
eGFR	estimated glomerular filtration rate
EOI	end of infusion
FAS	Full Analysis Set
FACIT-Fatigue	Functional Assessment of Chronic Illness Therapy-Fatigue
FDA	Food and Drug Administration
GOF	goodness-of-fit
HR	heart rate
IV	intravenous(ly)
LDH	lactate dehydrogenase
LOCF	last observation carried forward
MAVE	major adverse vascular event
MedDRA	Medical Dictionary for Regulatory Activities
OC	observed case
PD	pharmacodynamic
PK	pharmacokinetic
PNH	paroxysmal nocturnal hemoglobinuria

Abbreviation or acronym	Explanation
pRBC	peripheral red blood cell
PT	Preferred Term (MedDRA)
PTAEs	pre-treatment adverse events
QoL	quality of life
QTcF	QT interval corrected using Fridericia's formula
RBC	red blood cell
RR	respiration rate
SAE	serious adverse event
SAS®	Statistical Analysis Software®
SAP	Statistical Analysis Plan
SD	standard deviation
SDV	source data verification
SOC	System Organ Class (MedDRA)
TEAEs	treatment-emergent adverse events
t_{max}	time to maximum observed serum concentration
ULN	upper limit of normal
WHO-DRUG	World Health Organization Drug Dictionary
λ_z	apparent terminal-phase elimination rate constant

